9.5. Secondary endpoints/outcomes

- Cumulative peritonitis incidence in the LTAD and LVP groups
- Symptoms in LVP and LTAD groups assessed using the Ascites Q (74)
- Informal caregiver impact in LTAD and LVP groups assessed using the CRRS (75)

- Health resource utilisation in LTAD and LVP groups (modified AHCR (76-77) for community service use; hospital records for hospital service use using an inhouse designed questionnaire)
- Generic HRQoL and cost-utility analysis based on QALYs using EQ-5D-5L (78-79)
- Patient, caregiver and health care professional perceptions/perspectives of LTAD and LVP using qualitative methods

Table 2. Table of Endpoints / Outcomes

Objectives	Outcome measure	Timepoint(s) of evaluation of this outcome measure (if applicable)
Primary		
To assess whether palliative LTADs result in better health related quality of life (HRQoL) compared to LVP in patients with refractory ascites due to advanced cirrhosis. Secondary	Liver specific HRQoL assessed at 3 months with the SFLDQoL questionnaire	To be assessed at baseline and four weekly
To assess impact of LTADs and LVP on:		
Infections (especially peritonitis)	Cumulative peritonitis incidence in the LTAD and LVP groups	To be assessed at 3 months
Symptoms	Symptoms in LVP and LTAD groups assessed using Ascites Q	To be assessed at baseline and fortnightly for 3 months
Caregiver workload	Informal caregiver impact in LTAD and LVP groups assessed using CRRS	To be assessed at baseline and four weekly for 3 months

Health resource utilization	Health resource utilisation in LTAD and LVP groups: community service use (modified AHCR) and hospital records for hospital service use (inhouse designed questionnaire)	To be assessed at baseline and fortnightly, hospital service use at 3 months
	Generic HRQoL and cost-utility analysis based on QALYs using EQ-5D-5L	To be assessed at baseline and fortnightly
Explore perceptions of LTADs and LVP by patients, informal caregivers and healthcare professionals with qualitative interviews.	Patient, caregiver and health care professional perceptions/perspectives of LTAD and LVP using qualitative methods	Interviews (optional) to be conducted throughout the trial

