Concomitant medication review	X	X	X	X	X	X	Х
Ascites questionnaire (Ascites Q) completion (patient)	X	X	X	X	X	X	X
Liver specific HRQoL (SFLDQoL) questionnaire completion (patient)	X		X		Х		X
Generic HRQoL (EQ5D-5L) questionnaire completion (patient)	X	X	X	X	X	X	X
Care giver questionnaire (CRRS) completion (caregiver)	X		X		X		×

Community service use (modified AHCR) questionnaire completion (patient)		X	X	X	Х	Х	Х	Х
Hospital service use in house designed questionnaire completion (research team member)								X
Optional qualitative interviews (patients, informal caregivers and healthcare professionals) will be conducted throughout the study. Only one interview per participant			X	X	X	X	X	X

¹ PT and or INR and platelet count and diagnostic ascitic tap need to be checked within 7 +/-3 days of LTAD insertion; Spontaneous bacterial peritonitis defined as ascitic white cell count > 500 cells/mm³, and or neutrophil count > 250 cells/mm³ and or a positive ascitic fluid culture. (64)

² To be done in LVP group at each drainage as is current standard of care, and LTAD patients only if suspicion for peritonitis. In those with LTAD and clinical suspicion for peritonitis, take ascitic fluid sample for analysis from both from LTAD and via a separate ascitic tap

³ For LTAD only: Prior to LTAD insertion correct INR and platelet count as per local trust guidelines. If no local guidelines available use the following: if INR≥1.5 and platelet count ≤ $50x10^9$ 2 units of Fresh Frozen plasma and 1 -2 pools of platelets to be transfused prior to LTAD insertion

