Routine ascitic fluid analysis in the LVP group will be performed at each drainage as is currently standard of care. In the LTAD group, routine ascitic fluid analysis will not be performed due to the likelihood of growing skin contaminants (80), the clinical significance of which remains uncertain. In those with a LTAD, ascitic fluid analysis will **ONLY** be performed if there is clinical suspicion for peritonitis: fever, abdominal pain, increased white cell count, worsening hepatic decompensation or renal function. In such instances the ascitic fluid sample will be taken for analysis from both the LTAD as well as via a separate ascitic tap. Peritionitis will be diagnosed if ascitic fluid neutrophil count is > 250/mm³, and or ascitic fluid white cell count is >500/mm³ and or if ascitic fluid culture is positive. (9, 64) Peritonitis will be treated as per current guidelines. (9, 64) Development of peritonitis will not necessarily mandate LTAD removal. This needs to be decided on a **case-by-case basis** after discussion between site teams and the CI.

LTAD (Group 1) post drain insertion care (also see Figure 1)

- The research team will explain to the patient and informal caregivers how the LTAD will be used and provide them with the drainage kit, which will include at least two weeks supply of drainage bags. The Research teams will provide patients with the LTAD manufacturer information sheet and discharge letter, the latter also being sent to the GP and community nursing team. The discharge letter will state that patients have been discharged with a LTAD. LTAD manufacturer details are included in the discharge letter. An additional community nurse referral will be sent to the community teams with basic instructions on LTAD management.
- The research team will also contact the appropriate lead community nurse to update them. This will ensure that home visits can be organised by the community team to

perform recurrent drainage and arrange necessary disposal of clinical waste. The research team will also inform the LTAD manufacturer so that they can organise additional bespoke training and support for participants/informal caregivers if needed and ensure supply of drainage bags

• The patient and community teams will be provided with the contact number for the research team. The patients will also be provided with written information describing LTAD management should they be admitted to hospital out of hours so that clinical teams are aware.

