- Drainage of about 5L/week may not be sufficient for a small percentage of patients. In such instances patients can be admitted for supplementary LVP in hospital. This can be done via the LTAD (using specific adaptors). HAS will be administered as per LVP protocol. There will no need to take routine ascitic fluid samples from the LTAD and or do a routine diagnostic ascitic tap, unless suspicion for peritonitis. If patients are requiring frequent admission to hospital for supplementary LVP, then higher volume community LTAD drainage can be considered **on a case-by-case basis**, after discussion with the site PI, CI and community teams
- If a participant dies, the LTAD will be left in situ as per the usual practice. The community nursing team who will also follow standard procedures with regards to informing the undertakers of the presence of the LTAD.

Integrated Working Between Hospital and Community Teams

The success to implementing LTAD will be integrated working between hospital Gastroenterology/Hepatology, the community nursing teams (both the ones doing the drainage and the palliative teams), GPs and the patients/informal caregivers. Funding will be made available for sites to arrange up to two meeting with community teams to ensure engagement and collaboration. It can be difficult for HCP involved in the care of any patient near the end of life, especially in a cohort when death usually occurs in hospital. Research teams should be available to debrief community staff if needed.

For a summary of post-drain care, see Figure 1. Participant Flow Chart. A community standard operating procedure (SOP) will also be made available to all study sites.

16.2. Insertion Of Large Volume Paracentesis Drain (LVP), Group 2

At baseline participants randomised to the LVP group will undergo insertion in-line with standard of care. LVP involves insertion of a temporary drain by the usual medical team, usually drainage of 5-10 litres of ascites and use of intravenous (IV) human albumin solution (about 10 gms of albumin per 1-2L of fluid drained) (9, 64). If the total volume of fluid to be removed is < 5 litres then there will be no need to administer IV albumin. During LVP patients have routine bloods done in line with Table 3 Schedule of Assessments. A sample of ascites is sent at LVP, as per usual standard of care for white cell and neutrophil cell count and culture

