22.4. Potential Complications Of The Intervention

Table 5 below summarises the complications seen in the LVP and LTAD group in the REDUCe feasibility study. (46) Rates of complications were similar in both groups except a higher incidence of self-limiting leakage and cellulitis in the LTAD group (none required hospitalisation.

Complication	Recommended management	Incidence observed in the REDUCe trial		
		LTAD	LVP	
Leakage and cellulitis	Leakage usually self-limiting, if persists may need an extra suture. Continue ascites drainage via LTAD	Leakage/cellulitis 41%	Leakage/cellulitis 11%	
	Cellulitis usually results due to leakage and is again self-limiting. If persist may need a short course of antibiotics. Very rarely LTAD needs to be removed and can be re-sited			
Suspected peritonitis	Do a diagnostic tap for cell count and culture from peritoneum as well as taking sample from LTAD. Treat as per usual peritonitis guidelines. Decision to remove LTAD must be made on a case- by- case basis after discussion with patient/caregiver	6%	11%	
	Routine sampling of ascitic fluid from LTAD and or routine blood tests in asymptomatic patients is not recommended.			
Elevation in serum	Manage as clinically indicated	Serum creatinine (µmol/L) (median, IQR)	Serum creatinine (µmol/L) (median, IQR)	
creatinine		Baseline: 109 (79-141)	Baseline: 113.5 (89-134)	
		Week12: 104.5 (81-115.5)	Week 12: 127 (63-158)	
LTAD blockage	Admit to hospital and discuss need for replacement	0%	NA	
LTAD displacement	Admit to hospital if necessary and discuss need for replacement	6%	NA	
Bleeding	Usually self-limiting	0%	5%	

Table 5. Potential long-term abdominal drain and large volume-related complications observed
in the REDUCe feasibility trial

Unable to manage ascites symptoms despite draining 1-2L three times a week from LTAD	Will need LVP in hospital - drain ascitic fluid via LTAD using adaptor with human albumin solution as per standard LVP protocols	13%	NA
---	--	-----	----

Strategies to reduce complications related to the intervention (LTAD)

- Haemostatic function and ascitic fluid analysis (to exclude infection) to be done within seven +/- 3 days of LTAD insertion
- To reduce leakage/cellulitis ensure that
 - Ascites drained to dryness upon LTAD insertion in hospital using human albumin solution
 - Incisions are of appropriate size (may require a suture if too large)
 - The tunnelled portion of the LTAD is not under undue tension

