23.4. Statistical Plan and Analysis

All analyses will be performed in Stata version 17.0 (89) or later. A detailed statistical analysis plan (SAP) will be written up prior to data analysis.

Summary of baseline data and flow of patients

Participant flow will be depicted according to the CONSORT 2010 Statement. (90) Baseline data will be summarised by trial group, normally distributed variables described by their means/standard deviations, skewed continuous variables by their medians/interquartile ranges and categorical variables by their frequencies/percentages. Scoring rules for the study instruments will be detailed in the full statistical analysis plan.

Primary outcome analysis

The primary outcome will be analysed, following intention-to-treat principles, using a linear mixed effects model with fixed effects for time point (2 dummy variables), gender, continuous Child Pugh score, randomisation group, randomisation group by time point interaction and adjusting for SFLDQoL score at baseline, and with a random effect for participant to handle the correlation between repeated measurements. The model will be fitted using restricted maximum likelihood estimation. We will report the estimated treatment differences between LTAD and LVP groups at weeks 4, 8 and 12, their 95% confidence intervals and p values.

Secondary outcome analysis

Secondary outcomes will be analysed using mixed effects regression models appropriate to outcome type, adjusting for baseline measure of outcome, in addition to the fixed and random effects as detailed for the primary outcome analysis.

Subgroup analyses

Analysis will be stratified to include, but not limited to, liver prognostic scores, survival, development of peritonitis, ascitic fluid albumin level and presence of informal caregivers.

Participant population

All data collected on all randomised participants will be analysed in the arm to which they were randomised.

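### Peritonitis incidence is compared between arms under unequal sampling: LVP fluid is tested at every drainage, LTAD fluid only on clinical suspicion, which probably favours LTAD.

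*Protocol*

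**What the plan says.** **Outcome.** Protocol section 9.5 lists first among the secondary outcomes "Cumulative peritonitis incidence in the LTAD and LVP groups". Table 2 has it assessed at 3 months.

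**Sampling, LVP arm.** Section 16.1 (ascitic fluid analysis): "Routine ascitic fluid analysis in the LVP group will be performed at each drainage as is currently standard of care". Section 16.2 repeats this.

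**Sampling, LTAD arm.** The same part of 16.1: "In the LTAD group, routine ascitic fluid analysis will not be performed due to the likelihood of growing skin contaminants". Table 3, footnote 2, puts both rules in one line: "To be done in LVP group at each drainage as is current standard of care, and LTAD patients only if suspicion for peritonitis". The LTAD rule still applies when an LTAD patient is admitted for a supplementary LVP: "There will no need to take routine ascitic fluid samples from the LTAD" (16.1, community management). Table 5 in section 22.4 agrees: "Routine sampling of ascitic fluid from LTAD and or routine blood tests in asymptomatic patients is not recommended".

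**What triggers an LTAD sample.** Section 16.1 lists fever, abdominal pain, a raised white cell count, and worsening decompensation or renal function. Fluid is then taken from the drain and also by a separate tap.

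**Case definition.** Footnote 1 of Table 3 and section 16.1 use a neutrophil count above 250/mm³, a white cell count above 500/mm³, "and or if ascitic fluid culture is positive". No symptom is required, and 16.1 does not distinguish a drain sample from a tap sample.

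**The concern.** The definition is common to both arms but the chance of being tested is not. When a case is defined by a laboratory result alone, the number of cases found depends on how often fluid is sent. An LVP patient is tested at each drainage whatever their condition. An LTAD patient is tested only after a trigger. Episodes without a trigger can enter the LVP count and cannot enter the LTAD count.

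Section 8.3 names a possible increase in ascitic fluid infection as a main reason why LTADs are not used routinely in cirrhosis. Less complete detection in the LTAD arm would work against seeing that harm. The trial could report similar or lower peritonitis with LTAD partly because less was looked for. Section 23.4 also plans an analysis stratified by development of peritonitis, which would inherit the arm-dependent detection.

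The protocol gives a clinical reason for the difference in sampling. It does not mention the effect on the between-arm comparison and sets out no way of handling it.

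**Working it through.** **Figures in the protocol.** It states no sample size or power for peritonitis. The planned size rests on the HRQoL outcome: 93 per arm analysed and 186/(1 − 0.40) = 310 recruited, so 155 randomised per arm. The only peritonitis rates by arm are those of the feasibility trial: LTAD 6%, LVP 11%, from 36 randomised patients (8.3). With about 18 per arm, that is 0.06 × 18 = 1.1 and 0.11 × 18 = 2.0 patients, roughly one event against two.

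**Step 1: testing occasions.** Section 8 gives LVP every 10 to 14 days. Over 84 days that is 84/14 = 6 to 84/10 = 8.4 routine samples for an LVP patient who completes follow-up. An LTAD patient with no trigger has none after insertion. Zero is the floor for untriggered patients, not the expected number in the arm.

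**Step 2: effect of incomplete detection.** Let *s* be the share of laboratory-definable LTAD episodes that raise suspicion and so are sampled. Take LVP detection as complete (assumption). Then

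observed LTAD incidence = *s* × true LTAD incidence, and observed ratio = *s* × true ratio.

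The protocol does not give *s*, so the values below are assumptions. The true incidence is set at 11% in both arms. The last two columns give the chance of a nominally significant result in favour of LTAD (two-sided 5%, normal approximation).

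| *s* | Observed LTAD v LVP | True LTAD excess that would look like no difference (1/*s*) | 155 per arm | 93 per arm |
|---|---|---|---|---|
| 0.90 | 9.9% v 11% | 1.11-fold | 5.0% | 4.3% |
| 0.75 | 8.3% v 11% | 1.33-fold | 12.7% | 9.2% |
| 0.50 | 5.5% v 11% | 2.0-fold | 42.0% | 27.4% |

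With equal detection, the chance of a significant result in that direction would be 2.5%. The *s* that turns equal 11% rates into 6% v 11% is 6/11 = 0.55.

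**Step 3: untriggered positives in LVP.** A positive culture alone is enough, so repeated routine testing also accumulates culture-only positives. With an assumed positive rate *q* per untriggered sample, independent samples and 6 to 8 of them, the cumulative proportion is 1 − (1 − *q*)^m:

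- *q* = 0.5%: 3.0% to 3.9%
- *q* = 1%: 5.9% to 7.7%
- *q* = 2%: 11.4% to 14.9%

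These *q* values have no source in the protocol. The sum also assumes 12 weeks of follow-up for everyone, although 40% attrition is expected.

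**Step 4: the opposite effect.** A suspected LTAD case is sampled twice, and section 16.1 expects skin contaminants from drain fluid. A culture positive from the drain alone meets the definition as written. This can inflate the LTAD count, but only among patients already under suspicion.

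**The case against.** The strongest case on the other side has five parts.

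- **LTAD patients are not left unobserved.** The triggers include blood-test and organ-function changes that can occur without symptoms. Table 3 and section 22.5 schedule bloods, vital signs and pain assessment fortnightly in both arms, and community nurses may drain up to three times a week and report pain. This stands. A reader might infer that LTAD patients are never sampled unless symptomatic; the trigger list does not support that. What remains is that an episode with no trigger of any kind is still missed. (Table 5's advice against routine bloods in asymptomatic patients needs reconciling with that schedule.)
- **The direction is not certain.** Double sampling, culture-only positives and open-label suspicion (15.4) push LTAD ascertainment up. This stands as a qualification. A reader might infer a proven bias towards LTAD, but the protocol supports only a probable one.
- **The size is assumed.** This stands. A reader might take 3 to 15 percentage points from Step 3 as an estimate, but it follows from chosen values of *q*. The feasibility contrast of about one event against two cannot serve as a benchmark either.
- **A suspicion-only endpoint has its own bias.** It rests on unblinded judgement. It also drops LVP episodes that routine sampling found and that were treated before suspicion arose, while the LTAD equivalents may progress and count. This stands, and it rules out replacing the present definition.
- **The analysis model is a separate matter.** A reader might object that a repeated-measures model adjusted for baseline does not suit a single cumulative outcome, or that death competes with peritonitis. Section 23.4 says "Secondary outcomes will be analysed using mixed effects regression models appropriate to outcome type, adjusting for baseline measure of outcome". The wording allows a model suited to the outcome, and the detail belongs to the statistical analysis plan, which is not at hand. No finding is made on it.

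The sampling difference is also deliberate and clinically reasoned. That explains the practice but does not make the two counts comparable.

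**Conclusion.** The point holds in a limited form. As written, the first-listed secondary outcome is compared between arms with one laboratory definition and two sampling rules, and the protocol does not address the consequence. Untriggered positives can count in LVP and not in LTAD, so the comparison probably favours LTAD. Drain-plus-tap sampling of suspected LTAD cases offsets this to a smaller, unknown extent.

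The protocol gives no basis for a single figure. The 55% illustration rests on equal true rates of 11% and complete detection in LVP, and shows only that a moderate shortfall could produce a contrast of the size seen in the feasibility trial.

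This should be fixed, but it does not threaten the trial's main conclusion. Peritonitis is a secondary outcome without its own power calculation. The primary HRQoL outcome and the sample size are unaffected. So is the pilot's peritonitis criterion (Table 6), which is the percentage of LTADs removed for peritonitis and uses no between-arm comparison.

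**What to change.** Leave clinical sampling as it is and change what is recorded and reported.

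1. For each ascitic sample, record at the time it is taken, before the result is known, whether it was routine or suspicion-triggered (using the trigger list in 16.1) and whether it came from the drain or a separate tap. The case report form is not shown; if it already holds these items, only the reporting rule is needed.
2. Report the between-arm comparison two ways side by side: all laboratory-positive episodes as now defined, and suspicion-triggered, laboratory-confirmed episodes only.
3. Show separately the LVP positives found only on routine samples and the LTAD culture positives found only in drain fluid.
4. State in advance that similar or lower peritonitis with LTAD will not be concluded unless both comparisons support it.

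**Cost.** At most two data items per sample, plus wording in the protocol and analysis plan. The recording cannot wait for the analysis stage, because the reason for a sample cannot be recovered reliably later. The second comparison will have fewer events and a wider interval. It depends on unblinded suspicion and may tilt against LTAD, because routine LVP sampling catches and treats some episodes early. That is why both comparisons are needed and neither should replace the other.

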16.1. Participants Randomised To the Long-Term Abdominal Drain (LTAD) (Group 1)

Rocket Medical LTADs will be used for this study (see Figure 2 Long-term abdominal drain in situ, courtesy of Rocket Medical plc). Participants attending for LTAD placement will have their travel costs reimbursed.

Figure 2. Long-term abdominal drain in situ

LTAD Insertion

While at most sites, LTAD insertion will be performed by interventional radiology (IR), this is not essential. Individuals inserting LTADs outside of IR should undergo a period of supervised practice in IR and be assessed as competent to perform the procedure independently. Once a LTAD has been inserted it is recommended that the ascites is drained to dryness in hospital with human albumin solution (20%) administered as per LVP protocol. (9, 64) This makes subsequent community management of ascites easier. It must be ensured by the medical and research teams that appropriate transport is available for the participant to travel safely to the hospital if they are allocated to the LTAD arm.

Routine checking of haemostatic function is not recommended prior to LVP (9, 64). However, inserting a LTAD is a more invasive procedure as it involves tunnelling. Therefore haemostatic function (INR and platelet count) will be checked within the preceding 7 +/- days of LTAD and corrected as per local trust guidance. In absence of local trust guidance please correct as below (see also Table 3)

INR < 1.5	no FFP will be administered
INR > 1.5	2 units of FFP administered
Platelet count > 50x10 ⁹	no platelets transfused
Platelet count < 50x10 ⁹	1-2 pools of platelets transfused

Technique of LTAD Insertion

The LTAD will be inserted with ultrasound guidance after informed consent has been received. Technique for insertion has been described previously. (45)

The insertion technique is a combination of tunnelled and Seldinger technique. After confirming the site for insertion with the help of ultrasound, local anaesthetic will be administered. A small incision is made where the catheter will enter the abdominal cavity. A Seldinger needle will be inserted through the incision into the peritoneal cavity and a guide wire is passed through the Seldinger needle which will then be removed.

A second incision will be made approximately 5cm away from the 1st, where the catheter will exit the tunnel.

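### Table 3 footnote 3 and section 16.1 give different fallback rules for plasma and platelets before LTAD insertion when only one of INR and platelet count is past its cut-off

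*Protocol*

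**What the plan says.** Both passages put local trust guidance first and offer a fallback where there is none.

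- **Section 13.1, Table 3, footnote 3** (LTAD only): sites without local guidance are to "use the following: if INR≥1.5 and platelet count" is at or below 50x10^9, then "2 units of Fresh Frozen plasma and 1 -2 pools of platelets to be transfused prior to LTAD insertion". This is one sentence with one condition and one action covering both products.
- **Section 16.1, LTAD Insertion**: "In absence of local trust guidance please correct as below (see also Table 3"), followed by four separate lines. INR below 1.5: "no FFP will be administered". INR 1.5 or above: "2 units of FFP administered". Platelets above 50x10^9: "no platelets transfused". Platelets at or below 50x10^9: "1-2 pools of platelets transfused". Neither INR line mentions platelets, and neither platelet line mentions INR.

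The cross-reference runs one way only: section 16.1 sends the reader to Table 3, and footnote 3 does not mention section 16.1. Nothing states which text prevails.

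**The concern.** The cut-offs and quantities are the same in both places, so on a quick reading the two look like one rule. Their logic differs. The footnote ties both products to two conditions holding together; section 16.1 has two rules that work independently. For a patient with one value past its cut-off and the other not, what is done before insertion could depend on which page the site team has open.

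The protocol treats this step as a safety measure. Section 16.1 justifies checking and correcting haemostatic function by the more invasive, tunnelled nature of the procedure. Section 22.4 puts haemostatic checking first among its strategies for reducing LTAD complications. Section 22.2 lists bleeding directly related to the drain as an expected serious adverse reaction if it results in hospitalisation. Up to 35 sites are planned, so an instruction of this kind should read the same wherever it appears.

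**Working it through.** No sample size, power or error-rate figure is involved. The check compares the two rules over every combination of the two values.

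**Inputs**

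- Cut-offs, same in both passages: INR 1.5; platelets 50x10^9.
- Actions, same in both passages: 2 units of FFP; 1 to 2 pools of platelets.
- Scope, same in both passages: LTAD insertion where there is no local guidance.
- Footnote 3, read literally: if INR is 1.5 or above AND platelets are 50x10^9 or below, give FFP and platelets.
- Section 16.1: FFP if and only if INR is 1.5 or above; platelets if and only if the count is 50x10^9 or below.

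**Comparison, footnote read literally**

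| INR | Platelets (x10^9) | Section 16.1 | Footnote 3 | Same? |
|---|---|---|---|---|
| below 1.5 | above 50 | neither product | condition not met, nothing triggered | yes |
| 1.5 or above | 50 or below | FFP and platelets | FFP and platelets | yes |
| 1.5 or above | above 50 | FFP only | condition not met, nothing triggered | no |
| below 1.5 | 50 or below | platelets only | condition not met, nothing triggered | no |

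The passages agree in 2 of 4 combinations and differ in 2 of 4, namely those with exactly one value past its cut-off.

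**Does another reading of the footnote remove the difference?**

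1. *The conjunction read as 'or'.* One value past its cut-off would then trigger both products, against one in section 16.1. The same two combinations still differ, this time in the other direction.
2. *An implied 'respectively'* (INR governs FFP, platelet count governs platelets). All four combinations then agree. The footnote does not contain that word or any equivalent.

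Only the second reading reconciles the texts, and the reader has to supply it. The drafting elsewhere does not make it the obvious choice: where the protocol means either or both, it tends to write *and or*, as in footnote 1 of the same table and in sections 12.1 and 12.2. Footnote 3 has a plain *and*.

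The difference rests on sentence structure, with the relevant words and symbols intact in both places, so it is not an effect of how the table was extracted.

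**The case against.** The strongest reply is that this is loose drafting rather than two competing rules. Both texts share cut-offs, quantities and scope. The footnote names INR then platelets, and FFP then platelets, in matching order, which suits a compressed version of the section 16.1 lines. It opens with a general instruction to correct both values, which fits poorly with leaving a single abnormal value uncorrected. The pointer to Table 3 suggests that the authors saw one rule. All of this is fair as an account of what was probably intended. It does not settle what a site should do, because the footnote does not say it, and the table is a natural place for staff to look on the day.

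Three further limits stand in full:

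- **Silence is not a prohibition.** A reader might infer that the footnote forbids product when only one value is past its cut-off. It does not. It sets out one situation and says nothing about the others. In the two disputed combinations an explicit instruction in section 16.1 meets silence in the footnote.
- **Reach is narrow.** The issue touches only LTAD patients, at sites without local guidance, with exactly one value past its cut-off. The protocol gives no figure for any of these. Two of four combinations is a count of table cells and says nothing about the proportion of patients.
- **Bleeding differences between sites.** A reader might infer that the discrepancy will make bleeding outcomes differ between sites and so damage the trial's results. The document does not support that. Both passages already defer to local guidance, so practice may vary anyway, and bleeding is a safety event rather than a listed primary or secondary endpoint.

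**Conclusion.** The inconsistency is real and narrow. As written, the two fallback texts lead to different actions in two of the four INR and platelet combinations, those with exactly one value past its cut-off: section 16.1 gives one product, and the footnote read literally triggers none and leaves the case unaddressed. They agree in the other two.

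This rests on the literal wording of the footnote. If the authors meant 'respectively', the fault is an omission in the footnote and the two rules were intended to be the same; the text still needs correcting. The number of patients affected cannot be derived from the protocol and may be small. The sample size, the primary HRQoL comparison and the listed endpoints are unaffected. The point deserves action because it concerns a pre-procedure safety instruction and is easily put right.

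**What to change.** The clinical leads should decide which rule is intended and then do one of two things:

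- word Table 3 footnote 3 and section 16.1 identically, so that every combination of INR and platelet count is covered in the same way in both places; or
- replace the rule in the footnote with a reference to section 16.1, once the content of that section has been confirmed.

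Which rule is right is a clinical decision, and none is proposed here. The cost is a one-line protocol amendment and a note to sites. No change to data collection, sample size or analysis is needed.
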